#### Treatment-emergent increases in

Based on the sponsor's preliminary investigation, reducing the BCX9930 dose to 400 mg BID is anticipated to mitigate the risk of to subjects while maintaining the potential for demonstrating clinical benefit in the PNH patient population.

BCX9930 is expected to provide greater efficacy than the currently available C5 inhibitors by not only preventing intravascular hemolysis, but also by preventing C3 mediated extravascular hemolysis (EVH), thereby reducing symptom burden, reducing hemolysis, including EVH and breakthrough hemolysis (BTH), improving patient function, changing the administration route from intravenous (IV) to oral, and improving health-related quality of life. Study subject selection criteria, dose selection, and study monitoring assessments have been included to optimize benefit and to minimize the risk of toxicities to study participants. Regular monitoring of safety parameters, including AEs, clinical laboratory abnormalities, vital signs measurements, ECGs, and physical examination findings, will ensure that the

#### CONFIDENTIAL

benefit-risk profile supports continued dosing. In addition, an independent, program-wide data monitoring committee (DMC) will continue to provide oversight of the ongoing exposure of subjects to BCX9930 in this and other clinical studies. The overall benefit-risk balance is therefore considered to be acceptable.

## **3.** STUDY OBJECTIVE(S) AND ENDPOINT(S)

## 3.1. Study Objective(s)

#### **3.1.1. Primary Objective**

• To collect long-term safety and tolerability data in eligible subjects with PNH who previously received BCX9930 in a BioCryst-sponsored study and derived benefit from BCX9930 treatment.

#### **3.1.2.** Secondary Objectives

- To assess the continued effectiveness of BCX9930 in treatment of PNH during long-term administration.
- To evaluate patient reported outcomes (PROs) of long-term BCX9930 treatment.
- To collect PK, PD, and complement biomarker data in subjects with PNH for incorporation into meta-study models of population PK and PK/PD.
- To characterize the effects of BCX9930 in subjects with PNH by clinical measurements and PD and complement biomarkers.
- To evaluate biomarkers of complement activation during episodes of BTH.

## **3.2.** Study Endpoint(s)

#### **3.2.1. Primary Endpoints**

• Measurement of safety and tolerability by subject incidence of graded TEAEs, laboratory abnormalities, changes to vital signs, ECG results, and physical examination findings.

#### **3.2.2.** Secondary Endpoints

- Clinical PNH symptom assessments including fatigue, dyspnea, chest pain/discomfort, difficulty swallowing (esophageal pain), abdominal pain, headache, erectile dysfunction, hemoglobinuria, jaundice, incidence of BTH, and incidence of thromboembolic events.
- Clinical measurements of PNH (LDH, hemoglobin, haptoglobin, reticulocytes, transfusion requirements).
- PRO endpoints will include scores from the Quality of Life Questionnaire for patients with Aplastic Anemia / Paroxysmal Nocturnal Hemoglobinuria (QLQ-AA/PNH), Functional Assessment of Chronic Illness Therapy (FACIT) fatigue scale, and Treatment Satisfaction Questionnaire for Medication (TSQM).
- Concentration of BCX9930 in plasma at steady state in subjects with PNH.

#### **3.2.3.** Pharmacodynamic (PD) Endpoint

• PD and complement biomarker measurements will include PNH RBC and white blood cell (WBC) clone size, plasma Factor Bb and AP activity (as assessed via AP Hemolysis and AP Wieslab).

## **3.3.** Statistical Hypotheses

This is an open-label Phase 2 study without a control group; therefore, estimation is emphasized above hypothesis testing.

## 3.4. Study Design

This is an open-label phase 2 study designed to evaluate the long-term safety of daily oral treatment with BCX9930 in subjects who have participated in a previous BCX9930 trial. The study will also evaluate the long-term effectiveness and impact on quality of life or general well-being of BCX9930 treatment, and the subject's satisfaction with the medication.

Subjects who have provided written informed consent and who have participated in a BCX9930 study will require a screening visit if they have interrupted study drug  $\geq$  31 days,

Subjects who have provided written informed consent and who have participated in a BCX9930 study will not require a screening visit if they have interrupted study drug for between 1 and 30 days. However, they will require a baseline visit.

For subjects who roll over directly from another BCX9930 study without treatment interruption, no screening visit will be required. The final on-study visit assessments in the prior BCX9930 study will serve as the baseline assessments for this study; however, additional relevant baseline assessments for this study may be performed at the final on-treatment visit for the prior study as needed to satisfy enrollment criteria. Enrollment without treatment interruption into the current study will obviate the requirement for a follow-up visit in the previous BCX9930 study.

A subject may be enrolled once all eligibility criteria and study requirements are met. On-treatment study visits will occur on Day 1, then every 4 weeks up to Week 96 and then every 8 weeks until Week 144. Subjects with sCr elevations will be required to complete additional assessments at the investigational site, at a laboratory local to the subject, or via a home health service (where permitted and available). An independent DMC will review the safety data from this study in concert with the accumulating safety information generated across the BCX9930 clinical development program. The DMC convened and reviewed safety data once the first 4 subjects enrolled completed 12 weeks of dosing. Subsequent DMC meetings were and will be convened as detailed in the DMC Charter.

## 3.5. Number of Subjects

No sample size calculations were conducted for this open-label, long-term safety study. Approximately 200 subjects will be enrolled. Subjects will be eligible to receive BCX9930 for up to 144 weeks or until the Sponsor discontinues development of the product; whichever comes first. Both males and females will be enrolled. As reproductive toxicology studies have not yet been conducted, women of childbearing potential may be enrolled in this trial only if they meet and maintain strict contraceptive and pregnancy test requirements as listed in this protocol.

## **3.6.** Treatment

The active ingredient for this study is BCX9930, a small molecule inhibitor of Factor D supplied by BioCryst as 100, 200, and/or 250mg tablets. Earlier versions of this Protocol supplied a white or off-white powder in size 0 hard gelatin capsules. Additional details for the chemical and physical characteristics of BCX9930 may be found in the IB and investigational medical product (IMP) dossier (where applicable).

Subjects on earlier versions of the Protocol started treatment at the same dose level and regimen last administered to that subject in the prior study, and individually escalated their dose level as the physician felt appropriate. As of Protocol version 5, all subjects will receive 400 mg BID, and subjects on lower or higher doses will transition to 400 mg BID for continued participation. Where possible, the BCX9930 doses should be taken at the same times each day as close as possible to 12 hours apart (eg. 8:00 AM and 8:00 PM). If a subject does not take a BCX9930 dose at the scheduled time, the missed dose can be taken up to 6 hours after the scheduled dose time. Subjects will be instructed to bring all drug kits (both unused and used bottles) with them for each study visit.

## 3.7. Clinical Assessments

Planned study visits are Screening; Day 1; Weeks 4 through 96 at 4-week intervals, and Weeks 104 through 144 at 8-week intervals. Safety and tolerability will be evaluated through assessments of TEAEs, laboratory analyses (clinical chemistry, hematology, coagulation, and urinalysis), vital signs, ECGs, and physical examinations at the study visits indicated in the schedule of assessments (see Table 2).

- The questionnaires are to be administered first, then physical exam, then ECG and vital signs before lab samples, PNH clone sample, then PK, PD, concomitant medication and AE review, PNH symptoms assessment, transfusion review, and finally drug dispensing.
- A site is permitted to perform screening assessments over more than one screening visit. Rescreening of ineligible subjects will be approved or denied on a case-by-case basis by the Sponsor Medical Monitor. Retesting of specific assessments without entirely rescreening a subject may be permitted. A screening failure electronic case report form (eCRF) page will be completed for those subjects who do not proceed with study dosing.
- Subjects who dose escalate (under Protocol versions 1-3) will have an additional Dose Escalation visit 2 weeks (± 2 days) after each dose increase.
- Following discontinuation of study drug (either following completion of the treatment period or on premature discontinuation), subjects will return to the clinic for a minimum of 3 consecutive days for Hemolysis Monitoring visits. Following the 3 days of monitoring, if required, subjects may continue to be assessed every 2 days thereafter until the subject has stabilized to a new hemoglobin baseline.
- Subjects who permanently discontinue treatment will return to the clinic for Hemolysis Monitoring visits. Subsequently they will return to the clinic 3 weeks (21 ± 3 days) after the date of their last dose of BCX9930 for their End of Study assessments.

## Table 2:Study Design and Schedule of Assessments

Assessment	Screening Period a	Baseline Visit b	Treatment Period (Visit Schedule)		Unsahadulad	Discontinuation of Study Drug	End of Study
				,	Unscheaulea Visit Estlemine		Assessment
	Screening Visit (up to Day -28)	(Day 1)	Week 4 and Every 4 Wks up to Wk 96 c (± 3 days)	Week 96 and Every 8 wks Until Wk 144 d (± 6 days)	Visit Following BTH (within 48hrs or next working day)	Hemolysis Monitoring for at least 3 Consecutive Days e	3 Weeks (± 3 Days) After Last Dose of Study Drug
Informed consent f	X	Х					
Inclusion/exclusion criteria	X	Х					
Medical and medication history g	X	Х					
Weight/height/BMI h	X	Х	Х	Х			Х
Physical examination i	X	Х	Х	Х	Х	Х	Х
ECG j	Х	Х	Х	Х			Х
Pregnancy test (women) k	Х	Х	Х	Х			Х
FSH test (women) 	Х	Х					
Vital signs	Х	Х	Х	Х	Х	Х	Х
Clinical chemistry m / hematology/ coagulation/ urinalysis with microscopy n / iron, folate, B12 status labs o	Х	X	Х	X	X p	X p	Х
Urine for biomarkers q			Х	Х	Х	Х	Х
PNH symptoms assessment	Х	Х	Х	Х	Х	Х	Х
Assessment of blood transfusions	Х	Х	Х	Х			Х
Assess AEs, concomitant medications	X	Х	Х	Х	Х	Х	Х
PNH RBC and WBC clone size	Х	Х	Х	Х			
FACIT-Fatigue Scale		Х	X r	Х			
QLQ-AA/PNH		Х	X s	Х			
TSQM		Х	X t	Х			
PK blood sample		Х	Х	Х	Х	X u	
PK urine collection v			Х	Х	Х	Х	
PD blood sample		Х	Х	Х	Х	X u	Х
Study drug dosing w		←			X x		
Study drug accountability/ dispensing		X	Х	Х			Х

#### CONFIDENTIAL

Abbreviations: AE = adverse event; BID = twice daily; BTH = breakthrough hemolysis; BMI = body mass index; ECG = electrocardiogram;

FSH = follicle-stimulating hormone; FACIT = Functional Assessment of Chronic Illness Therapy; IMP = investigational medicinal product;

PD = pharmacodynamic; PK = pharmacokinetic; PNH = paroxysmal nocturnal hemoglobinuria; QLQ-AA/PNH = Quality of Life Questionnaire for Patients with Aplastic Anemia/PNH; RBC = red blood cell; TSQM = Treatment Satisfaction Questionnaire for Medication; WBC = white blood cell.

Aplastic Anemia/PNH, RBC = red blood cell, TSQM = Treatment Satisfaction Questionnaire for Medication, wi

a Screening visit is required for subjects who have interrupted study drug for > 30 days.

b The baseline visit should be within 28 days of the screening visit. For subjects directly rolling over from another BCX9930 study without treatment interruption, the final on-treatment visit in the prior BCX9930 study will be considered the baseline visit for this study.

c Visits should be every 4 weeks until a subject has completed a total of 96 weeks on treatment with BCX9930 (ie, weeks in this study plus weeks in the previous study).

d Subjects with sCr elevations will be required to complete additional assessments to monitor for potential renal toxicity at the investigational site, at a remote laboratory more convenient for the subject, or via a home health service (where permitted and available) as indicated in Protocol Section 11.3.4.1 and Protocol Section 13.9.5.3.

e Monitoring for the onset of hemolysis will be conducted after each subject stops BCX9930 treatment. Depending on the results, additional hemolysis testing may continue.

f Informed consent will be signed at the screening visit for subjects requiring a screening visit and will be signed for all other subjects at the baseline visit or final on treatment visit in the prior study (which serves as the subject's baseline visit in this study).

g Medical and medication history should include vaccination history status, assess risk of exposure, and arrange for any appropriate vaccinations to be administered based on local recommendations as well as individual subject considerations.

h BMI calculation and height at screening; weight is to be recorded at each in-clinic visit.

i Full physical examinations will be performed at screening and baseline; symptom-directed physical examinations will be performed at all post-baseline visits.

j All ECGs during the study will be single assessments. ECGs will be conducted every 12 weeks up to Week 96 (ie, Weeks 12, 24, 36, 48, 60, 72, 84, and 96) and every 24 weeks thereafter (ie, Weeks 120 and 144) during the treatment period.

k For women of childbearing potential, a serum pregnancy test will be administered at screening; urine pregnancy tests will be assessed at all subsequent visits. Starting at Week 100, women of childbearing potential will start performing urine pregnancy tests at home every 4 weeks (i.e., in between clinic visits). The results will be recorded by the site. If the urine pregnancy test is positive, the subject should contact the site immediately.

FSH will be measured at screening for any woman post-menopausal  $\leq 2$  years (this may be omitted if menopausal status was demonstrated with elevated FSH in the prior study). For women who do not undergo a screening visit, FSH may be assessed at baseline. In this case, the subject must have a negative urine pregnancy test at baseline prior to receiving study drug.

m Cholesterol and triglycerides will be measured every 12 weeks up to Week 96 (ie, Weeks 36, 48, 60, 72, 84, and 96) and every 24 weeks thereafter (ie, Weeks 120 and 144).

n Urine microscopy will be performed on urine collected at investigative site visits (and, where possible, at remote visits where the lab has appropriate on-site testing capability). Urine microscopy should be performed using the site's local laboratory (assuming appropriate on-site testing capability exists) in lieu of the central laboratory.

o Weeks 48, 96, and 144 only.

p Only limited hematology and clinical chemistry parameters measured as per Protocol Section 11.3.5 and Protocol Section 11.3.6.

q Urine will be collected at investigative site visits (ie, excluding remote visits) and aliquots frozen for possible future analysis of urine biomarkers.

r Completed at all treatment visits through Week 96 only.

## 27 of 64

## CONFIDENTIAL

#### CONFIDENTIAL

s Every 6 months through Week 96 only (ie, Weeks 24, 48, 72, and 96 only).

t Though Week 96 only (ie, at Weeks 12, 24, 48, 72, and 96 only).

u Single PK and PD sample collected 48 hours after treatment discontinuation.

v Spot urine samples will be collected for analysis of the concentration of BCX9930 and metabolites at investigational site visits (ie, excluding remote visits).

w The protocol-specified dosing regimen prior to this amendment was 500 mg BCX9930 BID. Under this amendment, subjects will take 400 mg BCX9930 BID. The IMP will be supplied by BioCryst as 100, 200, and/or 250 mg tablets to allow for dose adjustments if needed for the safety management of the subject.

x BCX9930 dosing should continue following BTH.

## 4. PLANNED ANALYSES

## 4.1. Interim Analyses

Interim analyses may be performed during the course of the study as needed to support regulatory filings and safety updates.

#### 4.1.1. Data Monitoring Committee

An independent DMC has been formed to review data from subjects on a regular basis to ensure the continued benefit-risk profile is favorable for each subject. The DMC has convened and reviewed safety data once the first 4 subjects enrolled completed 12 weeks of dosing. Subsequent meetings were and will be convened as detailed in the DMC Charter. The DMC may meet at any time should a safety issue arise that requires DMC input or a partial or full data review. A separate DMC charter maintained in the trial master file describes membership, roles, timing of DMC review, and responsibilities of the DMC members.

## 4.2. Final Analysis

The final analysis will be performed when the last subject has completed the final study visit, the data are cleaned, and the database has been authorized for analysis.

## 5. GENERAL CONSIDERATIONS FOR DATA HANDLING

This section addresses the definitions, algorithms, imputations, and conventions that will apply to the analysis and handling of the data in general. Rules that are data specific will be addressed in the detailed discussions of individual summary tables.

## 5.1. General Summary Table and Individual Subject Data Listing Considerations

Summary tables and listings will include "footers" providing:

- 1. Date and time of output generation.
- 2. SAS® program name that generates the output.
- 3. The name(s) and location(s) of any input dataset(s) used in the creation of the output.
- 4. Any other output-specific details that require elaboration.

The BioCryst Style Guide for Tables, Figures, and Listings will be used to guide the appearance of output. Version 9.4 or higher of the SAS system will be used to analyze the data and to generate tables, figures, and listings. All SAS programs prepared to analyze the data will be properly annotated to permit uninvolved outside statistical experts to replicate all the analyses specified in this statistical analysis plan (SAP).

The date of output generation links the output to the locked and archived database to allow replication of the results.

## 5.2. General Post Text Summary Table and Individual Subject Data Listing Format Considerations

Tables and listings will be numbered to reflect main levels of unique tables and listings and sub-levels of replicate tables and listings with two digits per level (eg, Table XX.YY.ZZ....).

- 1. The first level number should be consistent with the corresponding Clinical Study Report (CSR) appendix in which the tables or listings will appear. Following ICH-E3, all post text tables should have first level 14 and data listings should have 16.2.
- 2. For tabular presentations, subject accounting and final disposition, baseline, and demographic profile should appear as the first sub-level (Table 14.1 series). Efficacy should come next (Table 14.2 series), followed by safety, PK/PD, and other special-purpose sections. Similar conventions should be applied to the subject data listings (16.2.1 for discontinuation, 16.2.2 for protocol deviations, and so on).

The title should be complete, accurate, and concise. If convenient, the parameter and unit of measurement can appear in parentheses to conserve space in the body of the table. For example, a summary of orthostatic vital signs title could read "Summary of Sitting and Standing Blood Pressure (SBP) (mmHg) and Heart Rate (HR) (bpm)." Whether in the title or body of a table or listing, units must always be specified for all appropriate data. The last line of the title should provide the analysis group being summarized (eg, Intent-to-Treat Population or Per-Protocol Population).

In general, variables summarized and statistics reported should appear in the left-most column of a table. The columns for treatment groups should report the data from left to right for each treatment group (see Section 7), and (optional) all treated subjects, respectively. Any row with all zeros will not appear except

with reasons for disposition events or other similar lists of results (e.g. categorical urinalysis results). Summary tables clearly indicate the number of subjects to which the data apply, and unknown or not performed are distinguished from missing data.

In general, the listings should be sorted and presented by treatment group, subject number, parameter (where applicable), and date/time.

All tables and listings must have explanatory notes that give the definition of all derived variables and decodes for coded data. Footnotes will be in past tense for ease of incorporation into in-text tables in the CSR.

## 5.3. Data Management

The standard operating procedures (SOPs) of PharPoint, the selected data management and statistics vendor for this study, will be used. A data management plan was developed and approved prior to commencement of data entry. Data will be captured using the Medrio electronic data capture system. Electronic validation steps (edit checks) will be utilized, and data cleaning will occur in conjunction with each site. Prior to transfer of data provided by vendors (eg, laboratory data, PK data), a data transfer agreement including specifications for the type of file, definitions of variables, and contact information for the sending and receiving parties will be developed and finalized.

Data will be mapped to Study Data Tabulation Model (SDTM)-compliant datasets prior to creation of Analysis Data Model (ADaM)-compliant derived datasets for use in the creation of output. All analyses will be generated using SAS version 9.4 or above and in accordance with PharPoint SOPs.

## 5.4. Data Presentation Conventions

Continuous data will be summarized using the number of subjects with available data, mean, standard deviation (SD), standard error of the mean (SE), median, and minimum and maximum. Categorical data will be summarized using counts and percentages. Percentages are calculated using the total number of subjects per treatment group unless otherwise specified.

Unless otherwise specified, means and medians are formatted to one more decimal place than the measured value, SDs, SEs, confidence interval (CI) limits, and coefficient of variation (CV) to two more decimal places, and minimum and maximum values to the same number of decimal places. For categorical variables, the number and percentage of responses will be presented in the form XX (XX.X%) where the percentage is in the parentheses, except that 100% will be presented to three digits with no decimal. Dates will be formatted DDMMMYYYY and times will be formatted in 24-hour time as HH:MM. Partial dates will be handled as described in Sections 5.7.10 and 5.7.11. P-values and CIs will use a two-sided 0.05 significance level unless otherwise noted; p-values will be presented with three decimal places. Extreme p-values or CIs will be presented as "<0.001" and ">0.999" with the appropriate number of places.

All BCX9930 concentrations will be reported as provided by the concentration vendor.

Wherever possible, data will be decimal aligned.

CONFIDENTIAL

A table of contents at the end of this SAP provides the expected titles and numbers of the tables, listings, and figures of the final report. Changes to titles or numbering in the final report will not necessitate a revision to the SAP, nor will it be considered a deviation from planned analyses. Additional data listings supporting the tables will not be considered a deviation from planned analyses.

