14.3.4. Subject Demographic and Disposition Data

Demographic data and baseline characteristics including age, gender, race or ethnicity, height, weight, BMI, and PNH history will be summarized. Time from last BCX9930 dose to baseline will be summarized and listed as applicable.

Subject disposition will be presented for all subjects. The number of subjects who completed through each study visit and those that discontinued from the study will be provided. The reasons for early discontinuation also will be presented. A tabulation of the number of subjects exposed to study drug and duration of exposure will also be presented. Treatment adherence, dose interruptions, and reason for dose interruptions will be provided as summaries or listed as appropriate.

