## 7. STUDY POPULATION

## 7.1. Disposition of Subjects

Subject disposition will be presented for all subjects. The number and percentage of subjects who completed the study and discontinued from the study will be provided. The reasons for early discontinuation at any point also will be presented by planned treatment category. These data will also be listed by treatment and subject. Duration on study treatment during Study 201 and from the beginning of the previous study will also be provided.

The number and percentage of subjects included in the Safety, PK, and PD populations will be presented by treatment category.

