## 8.1.4.4. Disease Severity

Disease severity will be summarized by treatment category, visit, and by PNH symptom category (fatigue, dyspnea, chest pain/discomfort, difficulty swallowing, abdominal pain, headache, erectile dysfunction, hemoglobinuria, jaundice). The number of subjects with a symptom at each visit will be presented, along with a summary of the number of days with symptoms and the severity.

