## 9.2.1. Analysis of Abnormal Laboratory Values

Laboratory abnormalities will be graded according to DMID Adult Toxicity Table (draft version November 2007, see Protocol Appendix 1), with the exception of creatinine clearance and glomerular filtration rate, which will be graded using the National Cancer Institute (NCI) Common Terminology Criteria for Adverse Events (CTCAE) version 4.03.

Any graded abnormality that occurs following the initiation of study drug and represents at least 1-grade increase from the baseline assessment is defined as treatment emergent. The number and percentage of subjects who experience treatment-emergent graded toxicities will be summarized by panel, parameter, time point, and treatment category. Laboratory toxicity shifts from baseline to worst post-baseline grade will be summarized by panel, parameter, toxicity grade, and treatment.

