## 9.3. Bedside ECGs

Bedside ECGs are obtained as scheduled in Table 2.

Descriptive summaries of bedside ECG parameters (PR, QRS, QT, RR, and QTcF) and change from baseline will be presented by parameter, time point, and treatment category. ECG interpretation (normal, abnormal, abnormal clinically significant) will be presented by time point and treatment including "worst post baseline" (defined as Abnormal if ever Abnormal post-baseline, and otherwise Normal if always Normal post-baseline).

The number and percentage of subjects with  $QTcF \le 450$ , > 450 to  $\le 480$ , > 480 to  $\le 500$ , and > 500 msec; or changes of  $\le 30$ , > 30 to  $\le 60$ , or > 60 msec will be summarized by treatment category and visit along with worst post-baseline result. Unscheduled ECG results will be included in this summary table.

ECG results will be listed by treatment category, subject, parameter, and time point.

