## **10.** CLINICAL MEASUREMENTS AND SYMPTOMS OF PNH

#### **10.1.1.** Clinical PNH Symptoms

The following clinical parameters will be summarized with counts and percentages by treatment category and study visit: fatigue, dyspnea, chest pain/discomfort, difficulty swallowing (esophageal pain, dysphagia), abdominal pain, headache, erectile dysfunction, hemoglobinuria, and jaundice.

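### The SAP's default percentage denominator is all subjects in the group; nothing visible replaces it for by-visit symptom, laboratory and QTcF percentages, and the by-visit completion count is dropped

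*SAP*

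**What the plan says.** SAP 5.4 sets the general rule: "Percentages are calculated using the total number of subjects per treatment group unless otherwise specified". The groups displayed are the two C5-inhibitor categories of SAP 6.1. The same section summarizes continuous data on subjects with available data, so the two data types follow different conventions.

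Three sets of by-visit percentages fall under the rule, and none names its own denominator:

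- Symptoms, SAP 10.1.1: "The following clinical parameters will be summarized with counts and percentages by treatment category and study visit". Erectile dysfunction is in the common list, without restriction to men. SAP 8.1.4.4 adds, for the same symptoms, "The number of subjects with a symptom at each visit will be presented".
- Laboratory, SAP 9.2.1: "The number and percentage of subjects who experience treatment-emergent graded toxicities will be summarized by panel, parameter, time point, and treatment category".
- ECG, SAP 9.3: the QTcF categories "will be summarized by treatment category and visit along with worst post-baseline result".

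On disposition, Protocol 14.3.4 says: "The number of subjects who completed through each study visit and those that discontinued from the study will be provided". SAP 7.1 says: "The number and percentage of subjects who completed the study and discontinued from the study will be provided". SAP 7.1 adds reasons for discontinuation and duration of treatment, but no count by visit.

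Two other passages bear on the point. SAP 5.2 requires tables to show how many subjects the data relate to, and to separate results that are unknown or were not done from missing ones. SAP 12.2 places the display specifications in a separate document, which is not among those available here.

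**The concern.** Read literally, the rule keeps a subject who was not assessed at a visit in that visit's denominator. For a symptom or an abnormality, the subject is then in effect counted as free of it. As fewer subjects are assessed, a constant rate is printed as a falling one.

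The plan makes unassessed subjects likely:

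- Dropouts are not replaced (SAP 5.12.2) and missing data are not imputed (SAP 5.12.1).
- Protocol 11.1 has subjects without clinical benefit stop study drug, so those who leave need not resemble those who stay.
- Interim analyses are allowed (SAP 4.1), when later entrants will not have reached later visits.
- Footnote c of the assessment schedule counts prior-study weeks toward the 96 weeks of 4-weekly visits. If it is followed, some subjects who rolled over move to 8-weekly visits before study Week 96, while the analysis windows in SAP Table 3 stay 4-weekly to that point.

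The study is about long-term safety, and its primary endpoint names laboratory abnormalities and ECG results. A by-visit table that seems to show improvement only because fewer subjects were assessed would mislead. The count that would reveal this, completion through each visit, is the one SAP 7.1 leaves out.

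**Working it through.** The plan gives no figure to reproduce: there is no sample size calculation, retention rate, symptom prevalence or sex split. The check is a reading of each by-visit analysis against SAP 5.4, followed by an exact identity with assumed inputs.

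**Identity.** Let N be the group size, f the fraction assessed at the visit and p the rate among those assessed. The count is p × f × N, so the printed percentage is p × f × N / N = p × f.

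**Symptom or graded laboratory rate, p = 30% (assumed):**

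| Fraction assessed (assumed) | Printed, total N | Printed, assessed n |
|---|---|---|
| 90% | 0.30 × 0.9 = 27% | 30% |
| 80% | 0.30 × 0.8 = 24% | 30% |
| 70% | 0.30 × 0.7 = 21% | 30% |

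**QTcF.** The absolute categories cover every possible value. An unassessed subject belongs to none of them, so the category rows, including the normal one, sum to 100% × f: 80% if 80% are assessed. The remainder is visible only if a missing row is printed.

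**Erectile dysfunction.** With m the share of men and everyone assessed, the printed percentage is p × m. For 30% of men affected (assumed):

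- m = 40%: 0.30 × 0.40 = 12%
- m = 50%: 0.30 × 0.50 = 15%
- m = 60%: 0.30 × 0.60 = 18%

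The documents do not give m for the trial. Protocol 5.2 says only that the disease affects the sexes equally, and 40% to 60% is an assumed range. With a stable sex mix this is a constant scaling and not a trend. With 50% men and 80% assessed, the two effects combine to 0.30 × 0.50 × 0.80 = 12%.

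**Can the assessed rate be recovered?** Cells show a count and a percentage, so a reader needs only the number assessed.

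- Laboratory and QTcF: largely yes. Continuous laboratory results and ECG parameters, QTcF among them, are summarized by time point with the number of subjects with data (SAP 5.4, 9.2, 9.3).
- Symptoms: not directly. Symptoms have no continuous companion table. The laboratory n at the same visit is a proxy, and it does not give the number of men assessed.

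**Disposition.** Set side by side, Protocol 14.3.4 promises counts through each visit and SAP 7.1 gives overall completion and discontinuation. The display list in SAP 12.1 has one generic disposition table, whose title does not settle the matter.

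**The case against.** The best reply has four parts.

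**The display specifications may already set the denominators.** SAP 5.4 allows exceptions, and table shells often carry them. This stands as a limit on what can be concluded. The SAP text is silent, but nobody can say from it that the percentages will print this way.

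**SAP 5.2 and the companion tables already protect the reader.** This largely stands for laboratory and QTcF results. SAP 5.2 may well produce a missing or not-done row. It requires a number to be displayed, however, and does not change what the percentage is divided by. Symptoms remain exposed.

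**A fixed denominator is a recognized convention.** This stands for hematological response, where the fixed mITT denominator is a legitimate choice. It is weaker for symptoms and safety abnormalities, where it lowers the printed rate. It is also true that the assessed-only rate can improve over time because subjects who do poorly leave. Neither denominator is free of bias, so the numbers lost must be shown beside either one.

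**The sizes are assumed.** This stands. The identity is exact, but every input is illustrative.

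A reader might go further and infer that the trial's safety rates as a whole are understated, or that an interim cut would shrink them drastically. The documents do not support either inference. Whole-study adverse event incidence, worst post-baseline results, any-occurrence liver elevations, Kaplan-Meier estimates and hemoglobin means do not depend on by-visit denominators. No enrolment or timing is given for any interim cut.

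**Conclusion.** The point holds as a gap in the SAP text, of modest weight. The stated default, followed literally, gives by-visit symptom, graded laboratory and QTcF percentages equal to the assessed rate times the fraction assessed, and it puts women in the denominator for erectile dysfunction. Under the assumed inputs, 30% prints as 21% to 27% when 70% to 90% are assessed, and 30% of men prints as 12% to 18% when 40% to 60% are men. For laboratory and QTcF tables a reader can largely undo this; for symptoms not directly.

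The omission of the by-visit completion count from SAP 7.1 is a plain departure from Protocol 14.3.4 and needs no assumption.

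The consequence is limited to descriptive by-visit tables. The first part is conditional on the display specifications not overriding SAP 5.4.

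**What to change.** - **SAP 5.4:** state that by-visit symptom, laboratory and ECG percentages use subjects assessed at that visit, printed as n/assessed (%). Show the numbers discontinued and not yet at the visit alongside, so that selective dropout stays visible. Use assessed men only for erectile dysfunction. Keep total N for whole-study incidence.
- **SAP 7.1:** restore the number of subjects who completed through each visit.
- **SAP 8.1.2:** the fixed mITT denominator for hematological response may stay, with a visible row for subjects missing or discontinued.
- If the display specifications already contain these rules, a cross-reference from SAP 5.4 is enough for the denominators.

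The cost is a few sentences, one or two extra rows per table and a minor programming change. No new data are needed. The downside is slightly larger tables.
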